## C. Subset Analyses:

In order to determine the generalizability of the reported outcome measures, subset analyses will be performed for the specific population groups described in Table 9.

Table 7.         Subset Populations and Criteria for Subsets
--

Subset Population	Criteria for Subset

 
Gender
 
Secondary Anxiety Disorder Diagnosis
 
Prior Hospitalization for Major Depression
 
ATR Status
 
Baseline MT
 
	
 
Male, Female
 
Present, Not Present
 
Yes, No
 
ATR = 1, ATR = 2 thru 4
 
Median split of Baseline MT value
 
Quartile split of Baseline MT value
 

The criteria may be revised for any of these subsets and additional subsets declared based on the final inspection of the data distributions for pre-treatment study characteristics of the population at data lock.

Subsets will be examined using the following outcome measures only: HAMD24, MADRS, and CDRS-R.

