In addition to these data, the results of a large, federally-supported multisite study of the use of antidepressant medication for the treatment of adolescent major depression are also relevant to consider. This study was not specifically directed at the question of antidepressant medication monotherapy alone, rather the design was intended to examine the effectiveness of the combination of antidepressant medication with cognitive-behavior therapy (CBT). Nevertheless, examination of the medication alone treatment condition in this study provides important supportive information in an estimation of the anticipated standardized effect size in adolescents. The Treatment of Adolescent Depression Study (TADS) (March, et al., 2004) examined the benefit of the use of fluoxetine alone, CBT alone, or the combination of the two versus a placebo condition. In that report, the use of fluoxetine alone versus placebo was observed to demonstrate a standardized effect size of 0.68, similar in magnitude to the results of the Emslie and colleagues studies described above (Emslie, et al, 1997; 2002). It should be noted, however, that these studies with antidepressant medication utilized a treatment-naïve study population, excluding patients with treatment resistant depression.

Based on the aggregate evidence described here, it is anticipated that this study, if effective in demonstrating the superiority of NeuroStar TMS Therapy® compared to sham TMS in adolescent patients with treatment resistant major depressive disorder, may be expected to demonstrate a standardized effect size of approximately 0.50 to 0.60. As a stand-alone analysis, it is therefore expected that a sample size of 50 patients per treatment arm, at an alpha level of 0.05, should provide greater than 85% power to detect a statistically significant difference between the treatment groups. However, as noted further below, efficacy also may be established by analysis of the adolescent study data using a frequentist approach which borrows data from two prior adult RCTs in major depression using the NeuroStar TMS Therapy System.

44-02219-204, Rev C 21-JAN-2019

Page 4 of 28

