The null hypothesis will be tested in an analysis of covariance of the LV (value from 6-week visit unless it is missing, then LOCF used), using baseline score, and ATR medication resistance level as fixed effect covariates, adjusting for site differences using a random effect. As discussed elsewhere, the ATR medication resistance levels will group subjects categorically by number of medications which have shown an adequate degree of resistance for that subject. These resistance levels will be grouped into two categories in statistical model, 0-1 in the current episode or 2-4 in the current episode, unless the final distribution of ATR scores in the study population suggests another allocation would be more statistically appropriate. All tests are two-sided, at the 5% level. The primary outcome should be available and meaningful for nearly all subjects, so the main analysis will be by strict intention-to-treat as defined above. An analysis of observed cases only will be performed as a secondary outcome measure. A site by treatment interaction analysis will be done as a secondary analysis to see if there is significant heterogeneity in the effect of TMS across sites. In particular, we will examine site-specific treatment effects (with confidence intervals) to test for evidence of true reversal of effect.

Secondary outcomes include other continuous measures, and within-subject dichotomous variables as outlined in the efficacy variables described elsewhere in this protocol. The treatment effect null hypothesis will be tested by logistic regression on treatment group assignment with adjustment for site and ATR medication resistance level. In addition, the longitudinal symptom scores will be analyzed with a general linear model adjusting for baseline scores and ATR medication resistance level, using a saturated means model for time since baseline, with treatment effect parameterized by a linear effect in time. The correlation of scores within individuals over time will be handled by allowing a within-subjects residual covariance matrix selected by exploration of the sample semi-variogram, as described by Diggle, Liang and Zeger. If this exploration reveals that a mixed model approach will fit the covariance structure better, random effects will be included in the model. As in the main analysis, site by treatment interactions will be tested.

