## Section 6. Summary of Study Treatments and Concomitant Therapy

## A. Motor Threshold Determinations and TMS Stimulation Parameters:

Motor threshold determination is determined prior to initiation of treatment in each study phase and at the beginning of each reintroduction treatment occurring in Phase III. Ad hoc motor threshold determinations may be repeated at any time if clinically indicated based on the opinion of the attending physician. Information for the baseline motor threshold determinations prior to each study phase or reintroduction treatment block, and any ad hoc motor threshold determinations will be summarized as part of the general summary of TMS treatment parameters as noted in Table 7.

44-02219-204, Rev C 21-JAN-2019

Table 5. Motor Threshold and TMS Treatment Session Summary Information
--

Variable	Туре	Items
Motor Threshold Determinations		
• Baseline Motor Threshold at each study phase (all patients)	Continuous	Mean, SD, Median, Range
• Proportion of patients with a post- baseline motor threshold at each study phase	Categorical	N, % of patients

 
Number of post-baseline motor thresholds obtained
 
	Categorical	Number of ad hoc MTs (per study phase)
	Continuous	Mean, SD, Median, Range (for each ad hoc MT)

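### Baseline motor threshold is a continuous measure, but SAP 7.C examines it only by median and quartile splits, with no treatment-by-threshold interaction and no continuous term

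*SAP*

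**What the plan says.** SAP Section 7.C gives the purpose of the subset work: "In order to determine the generalizability of the reported outcome measures, subset analyses will be performed". In the table captioned Table 7 (the text above it calls it Table 9), baseline MT has two criteria, "Median split of Baseline MT value" and "Quartile split of Baseline MT value". The outcomes are limited: "Subsets will be examined using the following outcome measures only: HAMD24, MADRS, and CDRS-R". The section leaves room for change at data lock, on the basis of pre-treatment characteristics: "The criteria may be revised for any of these subsets and additional subsets declared based on the final inspection of the data distributions".

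SAP Section 6, Table 5 has a row that begins "Baseline Motor Threshold at each study phase (all patients". It types the variable as continuous and summarises it by mean, SD, median and range. That use is descriptive.

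Neither document names an interaction test for MT, or a model in which MT enters as a continuous covariate or modifier. Neither gives an expected interaction size, an SD or distribution for MT, or a power figure for this analysis. The nearest power statement concerns the main comparison in SAP Section 2.A: "a sample size of 50 patients per treatment arm, at an alpha level of 0.05, should provide greater than 85% power".

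**The concern.** MT is not an incidental baseline variable, because stimulation intensity is set relative to each subject's resting MT (protocol Section 10.1; SAP Section 3.A.1). Whether the benefit of TMS varies with MT is a sensible generalizability question, and it is a question about an interaction.

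Cutting MT at the sample median treats everyone in the same half as alike and discards the variation within halves. Quartiles discard less but leave very small groups. With 50 per arm, each half holds about 25 per arm and each quartile about 12 to 13. Two cuts (2 + 4 = 6 groups) on three outcomes give 18 subset results for one variable. Nothing says which cut governs or how differences between groups are to be judged.

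Two things are at stake: some of the ability to see a real dependence on MT, and the risk that noisy small-group estimates are read as a pattern. The primary conclusion is not at stake.

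**Working it through.** **Inputs from the documents.** 50 per arm, 100 in total, allocated 1:1 (SAP Sections 1.A and 2.A); expected standardized effect 0.50 to 0.60 (SAP Section 2.A); "All tests are two-sided, at the 5% level" (SAP Section 2.B).

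**Assumed, because the documents are silent.** MT roughly normal; a linear interaction; all 100 patients evaluable; the effect changing by g = 0.20 to 0.55 outcome SD per SD of MT.

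**Step 1: the plan's own power figure.** Power = Φ(d·√(50/2) − 1.96) = Φ(5d − 1.96).
- d = 0.60 gives Φ(1.04) = 85.1% (84.4% by noncentral t).
- d = 0.55 gives 78.5%.
- d = 0.50 gives 70.5%.

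The stated figure is reproduced at the top of the plan's effect range only. It concerns the main comparison and says nothing about MT.

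**Step 2: information kept by each form of MT.** For a linear interaction with a normal covariate, a median split keeps 2/π = 0.637 of the information, like losing about 36% of the sample. Quartiles keep 0.861 when used as a factor (3 df) and 0.856 when scored as a linear trend (1 df).

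**Step 3: power for the interaction.** With treatment coded ±½ and MT in SD units, the standard error of the interaction slope is 2/√100 = 0.2, so the noncentrality is g/0.2 = 5g.
- Continuous MT: Φ(5g − 1.96)
- Median split: Φ(5g·√0.637 − 1.96)
- Quartile factor: P(noncentral χ² on 3 df with noncentrality 0.861·(5g)² exceeds 7.81)
- Quartile trend: Φ(5g·√0.856 − 1.96)

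The last column is a simulation with F-tests (3,000 trials per setting), in the same order.

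| g | Continuous | Median split | Quartiles, 3 df | Quartile trend | Simulated |
|---|---|---|---|---|---|
| 0.20 | 16.9% | 12.3% | 10.6% | 15.0% | 16/13/10/16% |
| 0.30 | 32.3% | 22.3% | 18.7% | 28.4% | 31/22/18/27% |
| 0.40 | 51.6% | 35.8% | 31.2% | 45.6% | 48/33/28/42% |
| 0.55 | 78.5% | 59.3% | 55.5% | 72.1% | 75/54/51/69% |

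From g = 0.20 to 0.55, the formula losses against continuous MT are:
- median split: 16.9 − 12.3 = 4.6 points, rising to 78.5 − 59.3 = about 19;
- 3-df quartile test: 6.3, rising to 23.0;
- quartile trend: about 2, rising to about 6.

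The simulated losses are 3 to 21, 6 to 24 and 0 to 6. Taking formula and simulation together, the losses are about 4 to 20, 6 to 24 and 1 to 6 points.

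**Step 4: dependence on the MT distribution.** At g = 0.575, the simulated median-split loss is 19.6 points for normal MT, 12.9 for uniform and 24.5 for lognormal.

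**Step 5: what the splits would show with no interaction.** Suppose the effect is 0.55 SD at every MT and each subset is tested at two-sided 5% (the SAP does not say that it will be).
- Each half has about 48% power, so the two halves disagree on significance about 2 × 0.48 × 0.52 = 50% of the time.
- Each quartile has about 26% power, so the four give mixed results about 1 − 0.26⁴ − 0.74⁴ = 70% of the time.
- The 95% CI half-width within a quartile is about 0.83 SD, wider than the whole assumed effect.

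**The case against.** The strongest reply is that no planned power is being lost. The SAP describes subset displays in support of generalizability and specifies no interaction test for any subset, so the comparison above sets a test the plan could contain against others it does not contain. MT also appears neither in the success criteria (SAP Section 2.D) nor in the prioritized outcomes (SAP Table 6). Both statements are correct. They limit the importance of the point, but the chosen display still serves its stated purpose less well than MT used as measured.

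A reader might infer that the splits cost about 20 points of power in this trial. The documents do not support a single figure. A loss of that size from the median split needs g of about 0.5 or more. At 0.55 the modification is as large as the assumed main effect: TMS would do nothing one SD below mean MT and twice as much one SD above it. Smaller values give much smaller losses. Nor does one figure cover both cuts, since a trend across the quartiles loses little.

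A reader might also infer that the splits are why a real dependence would usually be missed. That does not follow. At g = 0.55 the median split detects it more often than not, and at g = 0.30 continuous MT also misses it about two times in three. The main constraint is the sample of 100.

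Finally, split tables are easy to read and assume no linearity. That stands, and is a reason to keep them as a display.

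**Conclusion.** The point holds as a low-priority improvement. Baseline MT is continuous, is examined only through median and quartile splits, and has no interaction test and no continuous treatment-by-MT term.

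The size is conditional on the assumptions listed in the working: about 4 to 20 points less interaction power for the median split, 6 to 24 for a 3-df quartile test, and 1 to 6 for a quartile trend. A different MT distribution moves these figures. Power for the interaction stays modest in any form unless the modification is nearly as large as the assumed treatment effect. The analysis is supportive, and a reader should not infer that the efficacy conclusion or any success criterion is affected.

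**What to change.** In SAP Table 7, for HAMD24, MADRS and CDRS-R, add a treatment-by-baseline-MT interaction to the ANCOVA with MT continuous (its main effect included). Report the interaction estimate with its 95% CI and the fitted treatment effect at the 25th, 50th and 75th percentiles of MT. Keep the median and quartile tables as a descriptive display, used to check linearity and not as separate tests.

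The cost is a line of SAP wording and one interaction term per outcome, using data already collected. The small downside is the linearity assumption, which the retained quartile display can check. The SAP should also say that power for this interaction is limited, so that a non-significant result is not read as evidence that the effect is the same at every MT.

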## D. Study by Study Assessment:

In order to assess the study populations in the meta-analysis, demographics for each study will be characterized as described in Table 10.

Table 8. Subset Populations and Criteria for Subsets
•

Variable Name	Туре	Items
Study	Categorical	Study 1
		Study 2
		Study 3
		Subset
Gender	Categorical	Male
		Female
		Percentage
Ethnicity	Categorical	Hispanic or Latino
		Not Hispanic or Latino
		Percentage
Race	Categorical	• White
		Black / African American
		Asian
		American Indian or Alaska Native
		Native Hawaiian or other Pacific Islander
		Other
		Percentage

## Section 8. Safety Analyses

## A. Data Safety Monitoring Board:

A Data Safety Monitoring Board is convened for this study. The DSMB will be provided with periodic reports including data specified in Attachment 2.

## **B.** Adverse Event Reporting:

The general methodology for adverse event collection is discussed in the study protocol. All verbatim reported adverse events are coded using the current version of the Medical Dictionary for Regulatory Activities (MedDRA). All adverse events are categorized by the investigative site staff by severity (3-tier) and by relatedness to the study device (5-tier).

Protocol-emergent adverse events will be reported separately for the Phase I, Phase II, the taper phase, and Phase III. For each study phase, tabular display of adverse events should be provided as follows:

- 1) Adverse events by system organ class and preferred term
- 2) Adverse events by system organ class, preferred term and severity
- 3) Adverse events by system organ class, preferred term and relationship to study device.

44-02219-204, Rev C 21-JAN-2019

Page 21 of 28

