Objectives	To evaluate the durability of benefit of TMS treatment over the course of 6 months in subjects who received clinical benefit from acute treatment course(s) (Phase III).
	To evaluate the benefit of daily, active, open-label TMS in Phase I subjects who did not receive protocol-defined clinical benefit; as new acute treatment (sham to active) or as extended treatment course (blinded active to open label active) (Phase II)

	Structural MRI (conducted at specific sites only): To utilize standard morphometric measures to determine structural changes in the brain associated with TMS treatment.
	Phase I: Total of 100 enrolled (50 Active/50 Sham) across sites
Number of Subjects	 Phase II: Subjects from phase I who did not receive protocol-defined clinical benefit from acute treatment will be offered open-label treatment (estimated to be 42 subjects) Phase III: Subject who did meet protocol-defined clinical benefit after acute treatment in Phase I or Phase II will be followed for 6 months post taper (estimated to be 37 subjects) Structural MRI subset: Approximately 25% of subjects of the Phase I population.
Diagnosis and Main Inclusion Criteria	 Male or female outpatients, age 12-21, meeting DSM-5 diagnosis of Major Depressive Disorder, single or recurrent course of illness, of moderate or greater symptom severity CGI-S score ≥ 4 HAMD₂₄, item 1 ≥ 2 and total score at least 20 at screening At the end of the baseline visit, subject must have a HAMD24 score of ≥ 18 and change in score may not be ≥ 25% decrease from that seen at the screening visit Duration of current episode of depression ≥ 4 weeks and ≤ 3 years Resistance to antidepressant treatment in a discrete illness episode defined by the Antidepressant Treatment Record (ATR): Resistance to treatment defined by ATR level 1 through 4 in current episode. If insufficient number of trials in a previous episode Subjects who have been unable to complete an antidepressant trial of adequate dose and duration due to intolerance to antidepressant therapy may be included if they have demonstrated intolerance to ≥ 4 antidepressant medications within one discrete illness episode (current or a previous episode as defined above) For any subject currently receiving antidepressant medication, the clinician must determine that insufficient benefit is being received from this treatment and it is clinically appropriate to discontinue the existing antidepressant.

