9.2 Secondary objectives

Phase I

To evaluate the acute safety of TMS in adolescent subjects.

Phase II

To evaluate the benefit of daily, active, open-label TMS in Phase I subjects who did not receive protocoldefined clinical benefit from their assigned treatment condition in Phase I; either as new acute treatment (sham to active) or as extended treatment course (blinded active to open label active).

Page 24 of 61

Phase III

To evaluate the long term safety of TMS in adolescent subjects.

To evaluate the durability of the acute clinical benefit of TMS treatment over the course of 6 months among subjects who received protocol-defined clinical benefit from their initial acute treatment course(s).

10 Study Design

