## 3. Phase III (Long Term Follow up):

Subjects who achieve protocol-defined clinical benefit from treatment in Phase I or Phase II will be followed for 6 months after treatment.

If a subject experiences re-emergence of depressive symptoms, an acute TMS retreatment course will be initiated. The TMS retreatment course will continue up to 6 weeks until symptom score is at or below Phase III entry score. Each successful retreatment is followed by a 3-week taper. Subjects could receive retreatment on more than one occasion; therefore, any subject could receive up to 72 treatments in Phase III over 6 months, in addition to Phase I and II exposure.

44-02219-204, Rev C 21-JAN-2019

Page 8 of 28

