  approximately 2 weeks post previous months visit.
- i. Those AEs occurring following informed consent signature through 30 days after the last study visit will be collected.
- j. Medication treatment for emergent insomnia and emergent anxiety is permitted (refer to protocol for usage allowance).
- k. A Motor Threshold Determination (MT) is to be performed prior to the administration of the first TMS treatment in each treatment course. In addition, motor threshold may be repeated at any time during the course of the active TMS treatment sessions based on clinical assessment of the supervising physician.
- I. TMS retreatment is to occur if the CGI-S increases by 1 from the score at entry into Phase III and is confirmed one week later.

44-02219-204, Rev C 21-JAN-2019

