#### 1. All Enrolled Population:

The all-enrolled study population is defined as those individuals who signed an informed consent, and were subsequently randomized in the study (this population includes both the evaluable and the non-evaluable patient samples). The reasons for patient non-evaluability will be itemized in the final study report, however, no other summary statistics of demographics or clinical outcomes will be reported for the all-enrolled study population. This population will constitute the safety analysis dataset.

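### SAP 8.B does not separate Phase III adverse events by TMS retreatment and states no denominator, so rates of TMS-specific events during repeat courses would be understated by an amount that depends on the unknown retreated share

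*SAP*

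**What the plan says.** SAP 8.B names four strata: "Protocol-emergent adverse events will be reported separately for the Phase I, Phase II, the taper phase, and Phase III". It continues, "For each study phase, tabular display of adverse events should be provided as follows", and lists three tables: by term, by term and severity, and by term and relationship to the device. It gives no denominator for any of them. The only safety population in the SAP is the all-enrolled set of randomized subjects (Section 3.C.1): "This population will constitute the safety analysis dataset".

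TMS in Phase III is conditional. SAP Section 3.A.3 says: "If a subject experiences re-emergence of depressive symptoms, an acute TMS retreatment course will be initiated". The Phase III schedule adds: "TMS retreatment is to occur if the CGI-S increases by 1 from the score at entry into Phase III", subject to confirmation a week later. Section 3.A.3 also says "Subjects could receive retreatment on more than one occasion" and puts the Phase III maximum at 72 treatments. Retreatment uses the known-active coil (Protocol 13.2).

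The Phase III safety objective in Protocol 9.2 reads: "To evaluate the long term safety of TMS in adolescent subjects". SAP 1.C likewise lists long-term safety as a secondary objective.

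**The concern.** Phases I and II are treatment phases, so a per-phase rate there describes subjects on a course. Phase III is not uniform: one entrant may receive no stimulation, while another may receive up to twice the 36-session Phase I maximum. Events caused by stimulation, such as application site pain or muscle twitching, would mostly arise during retreatment. A rate for the whole block also counts subjects who had no sessions.

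The protocol states in Section 8.4 that long-term effects of TMS are not known, and retreatment is where repeat exposure accumulates. From the planned tables a reader could not tell how often retreated adolescents had an event. A Phase III rate set beside those of Phases I and II would compare partly untreated subjects with fully treated ones.

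**Working it through.** The documents give no Phase III event rate, retreated share or dilution factor, so there is no design figure to reproduce. The inputs do check:

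- Maximum Phase III exposure: 2 × (30 + 3 + 2 + 1) = 72, as in SAP 3.A.3.
- Application site pain in the adult trial (Protocol 8.4, Table 1): 59/165 = 35.8% active, 6/158 = 3.8% sham.
- Expected Phase III entrants (Protocol Study Summary): 37.
- Retreated share: the only figure is 36.2% over 12 months in the adult naturalistic study (Protocol 8.1). Scaled to 6 months at a constant hazard (an assumption), it is 1 − √(1 − 0.362) = 20.1%.

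Let r be the share of entrants retreated, p1 the event risk if retreated and p0 the risk if not. With all entrants as denominator (also an assumption), the block shows r·p1 + (1 − r)·p0. The understatement is p1 divided by that quantity, which is 1/r when p0 = 0.

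For application site pain, with p1 = 35.8%:

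| Retreated share r | Retreated of 37 | Block rate, p0 = 0 | Factor | Block rate, p0 = 3.8% | Factor |
|---|---|---|---|---|---|
| 20.1% | 7.4 | 7.2% | 5.0 | 10.2% | 3.5 |
| 36.2% | 13.4 | 12.9% | 2.8 | 15.4% | 2.3 |
| 50% | 18.5 | 17.9% | 2.0 | 19.8% | 1.8 |
| 70% | 25.9 | 25.0% | 1.4 | 26.2% | 1.4 |

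Example, r = 36.2% and p0 = 3.8%: 0.362 × 0.358 + 0.638 × 0.038 = 0.154, and 0.358/0.154 = 2.3.

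In counts, at 20–36% retreated, about 3 to 5 subjects with site pain (7.4 × 0.358 = 2.7; 13.4 × 0.358 = 4.8) would be divided by 37 rather than by about 7 to 13. With p0 = 0, the factor reaches 3 only when r is at most one third. For an event unrelated to TMS, p1 = p0 and the factor is 1 at any r.

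Whether another planned output supplies the missing rate:

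- SAP 8.D, on headache and pain near the treatment site, covers Phase I only.
- SAP 8.C lists serious events with narratives. It gives no rates for common non-serious events.
- The relatedness table in 8.B gives a count of device-related events but no retreated denominator.
- SAP 6.A summarizes motor threshold by reintroduction block, and the Phase III schedule times audiometry and the C-SSRS around retreatment. The plan thus recognizes retreatment as a distinct exposure, but not in its adverse event tables.

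**The case against.** Several points on the other side stand.

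- **Denominator.** A reader might infer that the SAP divides Phase III counts by all entrants, or, because the only safety set is all randomized subjects, by 100. The second reading would give 100/13.4 = 7.5-fold to 100/7.4 = 13.4-fold at 36–20% retreated with p0 = 0. The SAP states neither, so neither can be charged to it. What can be said is that the denominator is missing.
- **Retreated share.** A reader might also infer that only a minority will be retreated and that dilution is therefore several-fold. The 36.2% comes from adults who could be maintained on antidepressants and were followed for 12 months. Six months of follow-up points lower. The absence of antidepressants points higher, and the one-point CGI-S trigger may too. The share in this trial is unknown.
- **Event rate.** The 35.8% is a first-course adult rate. Adolescents who have already completed a course with benefit may tolerate repeat sessions better, and SAP 8.D itself looks for accommodation. The percentages are illustrations, not projections.
- **Existing safeguards.** Device-related events in Phase III can be counted, serious events are described individually, and Phase III analysis is descriptive (SAP 7.A). No test or success criterion depends on this table. A table over all followed subjects also does say something about long-term safety after TMS.

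These points limit the size and consequence of the problem. They do not supply a retreated denominator or a split between time on and off treatment.

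**Conclusion.** The concern holds as a reporting gap. Phase III adverse events are planned as one block, active TMS in that block is conditional, no denominator is stated, and no other adverse event analysis separates retreatment from follow-up. Unless nearly every entrant is retreated, a rate over all entrants understates TMS-specific events during repeat courses. For events of the site-pain type the factor is about 2.3 to 5 if 20–36% are retreated and 2 or less if half or more are. Events unrelated to TMS are not affected. These factors assume all entrants as denominator, the adult event rates, and a background between zero and the sham rate. The documents do not support an unconditional several-fold claim, and the Phase I efficacy and safety comparisons are untouched.

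**What to change.** In SAP 8.B, split Phase III adverse events by onset date into:

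- (a) retreatment periods, from the first retreatment session through the end of that course's taper, with retreated subjects as denominator and the number of courses and treatment-weeks shown;
- (b) follow-up without TMS, with all Phase III entrants as denominator.

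State both denominators and give the term, severity and relatedness tables for each part.

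State also that events in a post-retreatment taper count under (a), not under the separate taper stratum, which should hold only tapers after Phase I or Phase II. SAP 8.B leaves this open, and without the rule, events during taper sessions could fall into the untreated period. SAP 3.A.3 ties the taper to a successful retreatment, whereas Protocol 10.1 and the Phase III schedule attach it to every one. Those passages must be reconciled so that the window has a defined end.

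The data are already collected: event dates under Protocol 16.4 and session details under Protocol 17.3. The cost is one more set of descriptive tables. The retreated group may be small, about 7 to 13 of 37 under the adult-based assumption, so its percentages will be imprecise and should be shown with counts. No visit, treatment or clinical rule changes.
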